7.4 GENERAL AND DIETARY RESTRICTIONS

Exposure of the BCC lesions to sunlight should be avoided or minimized throughout the whole study course. Subjects with sunburn within the treatment areas cannot be included until fully recovered. The consumption of alcoholic beverages should be moderate. The use of certain concomitant medications is restricted (for further information, see [Sections 4.3, 4.4](#) and 6).

8 ADVERSE EVENTS

8.1 DEFINITIONS

8.1.1 Adverse events

The term **AE** covers any unfavorable and unintended sign, symptom, syndrome, or illness that develops or worsens during the period of observation in the clinical study. No causal relationship with the IMP or the medical device or with the clinical study procedure is implied by the use of the term “adverse event”. Clinically relevant abnormal results of diagnostic procedures including abnormal laboratory findings (e.g. requiring unscheduled diagnostic procedures or treatment measures, or resulting in withdrawal from the study) are considered to be AEs.

Maximum intensity should be assigned to one of the following categories:

- **Mild:** For example, an adverse event which is easily tolerated by the subject, causing minimal discomfort and not interfering with everyday activities.
- **Moderate:** For example, an adverse event which is sufficiently discomforting to interfere with normal everyday activities.
- **Severe:** For example, an adverse event which is incapacitating and prevents normal everyday activities.

The routine evolution of the condition under treatment may be measured by efficacy parameters. However, if there is a worsening of a sign or symptom of the condition under treatment and the outcome fulfills the definition of an “SAE”, it must be recorded as such (see [Section 8.1.2](#)).

Examples of AEs include one of the following or a combination of two or more of these factors:

- A new sign, symptom, illness, or syndrome.
- Worsening of a concomitant illness.
- An effect of the IMP, including comparator or concomitant medication.
- An effect of the medical device, if applicable
- An effect of an invasive procedure required by the protocol.
- An accident or injury.

AEs can be categorized as “non-serious” and “serious” (see [Section 8.1.2](#)).

Surgical procedures themselves are not AEs; they are therapeutic measures for conditions that require surgery. The condition for which the surgery is required is an AE, if it occurs or is detected during the study period. Planned surgical measures and the condition(s) leading to these measures are not AEs, if the condition(s) was (were) known before the period of observation (see [Section 8.2](#)) and did not worsen during the study. In the latter case, the condition should be documented as medical history.

8.1.2 Serious adverse event

Any adverse event should be assigned to be unrelated or related to either the study medication, the medical device (BF-RhodoLED®, or both, as this will be important for evaluation of the safety of BF-200 ALA or the lamp.

In general, an **SAE** is one that occurs at any dose (including overdose) and

- Results in death.
- Is life-threatening.

“Life-threatening” means that the subject was at immediate risk of death at the time of the SAE; it does not refer to an SAE that hypothetically might have caused death if it were more severe.

- Requires inpatient hospitalization or prolongation of existing hospitalization.

This means that hospital inpatient admission or prolongation of hospital stay were required for the treatment of the AE, or that they occurred as a consequence of the event.

- Results in persistent or significant disability or incapacity.

“Persistent or significant disability or incapacity” means a permanent or significant and substantial disruption of a person’s ability to carry out normal life functions”.

- Is a congenital anomaly or birth defect.
- Is an important medical event.

Medical and scientific judgment should be exercised in deciding whether expedited reporting is appropriate in situations where none of the outcomes listed above occurred.

Important medical events that may not be immediately life-threatening or result in death or hospitalization but may jeopardize the subject or may require interventions to prevent one of the other outcomes listed in the definition above should also usually be considered serious. Examples of such events include allergic bronchospasm requiring intensive treatment in an emergency room or at home, blood dyscrasias, or convulsions that do not result in inpatient hospitalization, or the development of drug dependency or drug abuse.

A diagnosis of a second cancer during the course of a treatment should be considered as medically important.

The term “severe” is often used to describe the intensity (severity) of a specific event (as in mild, moderate, or severe myocardial infarction); the event itself, however, may be of relatively minor medical significance (such as severe headache). This is not the same as “serious”, which is based on the outcome or action criteria usually associated with events that pose a threat to life or functioning. Seriousness (not severity) serves as a guide for defining regulatory reporting obligations.

8.1.3 Alert terms and other reasons for expedited reporting to Pharmacovigilance

No particular AEs are subject to reporting as alert terms in this study.

In the pivotal AK and BCC clinical trials conducted in the EU (ALA-AK-CT002 and ALA-AK-CT003 with BF-200 ALA and various light sources, or ALA-AK-CT007 and ALA-BCC-CT008 utilizing BF-200 ALA in combination with BF-RhodoLED®) almost all subjects developed local, treatment-related phototoxicity reactions. However, most of these phototoxic reactions were mild to moderate, and occurred only temporarily in most cases.

The most common signs and symptoms at the application site are irritation, erythema, pain, and edema. The intensity of these effects is dependent on the lesion site and the type of illumination used for PDT. The increased effects correlate with the higher clearance rate of narrow spectrum lamps such as BF-RhodoLED®. Most adverse reactions occur during illumination or shortly afterwards. The symptoms are usually of mild or moderate intensity (investigator's assessment on a 4-point scale), and last for 1 to 4 days in most cases. However in some cases, they may persist for 1 to 2 weeks or even longer. In rare cases, the adverse reactions may require interruption or discontinuation of the illumination.

As most AEs observed were of mild to moderate severity and as we have no reason to expect any other side effect than stated above, no alert terms and other reasons for expedited reporting to Pharmacovigilance are defined.

For details on known adverse reactions see Ameluz® PI (30) and current Investigator's Brochure.

Furthermore, all adverse events reported in the past were not directly related to BF-RhodoLED® but either to the medication or PDT. Therefore, we do not expect any adverse events that relate directly to BF-RhodoLED®, provided that it is properly used as described in the user manual.

Although not regarded as an SAE, any pregnancy in a female subject occurring during treatment with the IMP must be reported to the sponsor immediately. Information related to the pregnancy must be given on a "Pregnancy report form" that will be provided by the sponsor. This information must be provided regardless of the decision to withdraw the subject from the study or discontinue the treatment.

8.1.4 Investigational product complaints

Complaints associated with the IMP quality must be reported to the sponsor/CRO.

8.1.5 Investigational medical device complaints

Complaints associated with the medical device BF-RhodoLED® (Adverse Device Effect - ADE) must be reported to the sponsor/CRO.

8.2 PERIOD OF OBSERVATION

For the purposes of this study, the period of observation for collection of AEs extends from the time the subject gives informed consent until the end of the clinical observation period of the study at Visit 5 or Visit 8 (in case of re-treatment with a 2nd PDT cycle).

At the FU visits, any local AEs (i.e., AEs affecting skin health in the treatment fields), which might impair proper assessment of the recurrence of the treated sBCC lesions, or other clinically relevant

events at the investigator's discretion, or conditions that may be relevant for proper assessment of the recurrence of the treated BCC lesions) should be documented including any recurrent BCC lesions and any new lesions (AK, other NMSC, and melanoma) (see [Section 7.2.3](#)).

Relevant SAEs or related SAEs (SARs) should be documented until the end of the FU period (60 months after completion of the 1st PDT cycle (Visit 5)).

If the investigators detect an SAE in a subject after the end of the FU period, and considers the event possibly related to prior study treatment or procedures, they should report this event to the pharmacovigilance department of the sponsor.

8.3 DOCUMENTATION AND REPORTING OF ADVERSE EVENTS

8.3.1 Documentation and reporting of adverse events by investigator

All AEs as well as any SAE that occur during the observation period (see [Section 8.2](#)) must be documented in accordance with the instructions for the completion of AE reports in clinical studies. During the follow-up phase only local AEs or conditions affecting skin health in the treatment fields and the surrounding treatment area have to be documented which might thus impair a proper assessment of the recurrence of the treated AK lesions, or other clinically relevant events at the investigator's discretion as well as any relevant SAE or SAR during the follow-up phase, respectively. If possible, AEs should be assigned to be either unrelated or related to the study medication or the medical device (BF-RhodoLED[®]), or both.

These instructions will be provided to the investigator.

The following approach will be taken for documentation:

- **All AEs** (whether serious or non-serious, or considered as an alert term) must be documented during the clinical observation period.
- If the AE is serious (see [Section 8.1.2](#)), the investigator must complete, in addition to the "Adverse Event" page in the eCRF, a "Serious Adverse Event/Expedited Report for Combination Products from a Clinical Trial" form at the time the SAE is detected. This form must be marked as "initial" and be sent immediately (within 24 hours) to the sponsor's Pharmacovigilance department by email or fax (according to Biofrontera's Standard Operating Procedure (SOP)). SAEs must be identified as such in eCRF by stating the applicable SAE criteria that were met. During the follow-up phase only relevant SAEs or SARs according to the investigators decision have to be reported.
- When a "significant overdose" of IMP occurs without an AE or in other situations where the sponsor requires an expedited report without an AE (see [Section 8.1.3](#)), the investigator should only complete a "Serious Adverse Event/Expedited Report from a Clinical Trial for Combination products" form. It should be clearly stated that no adverse event was observed. Instructions on where to send this form will be provided. In this case, there is no need to complete the "Adverse Event" page in the eCRF.
- The following details regarding AEs are required: diagnosis, location (inside/ outside treatment field(s)/ treatment area), source (study medication/device/both), time frame (by providing start/stop date and time), intensity (see [Section 8.1.1](#)), outcome, seriousness criteria

(if applicable), and if the AE is related to IMP only, medical device only, or cannot be ambiguously assigned to one of both. Detailed instructions on AE documentation will be handed out by the sponsor.

- The causality/relatedness of AEs has to be assessed:
 - **UNRELATED**: AEs that are judged to be clearly and incontrovertibly due to a cause other than the IMP/BF-RhodoLED® and study procedure (concurrent illness etc.).
 - **UNLIKELY RELATED**: the temporal sequence is atypical and the AE does not follow a known pattern of response to IMP/BF-RhodoLED®; another causative factor is present but causal role of the study drug cannot be excluded.
 - **POSSIBLY RELATED**: either an event that is temporally associated with the use of the IMP/BF-RhodoLED® or a known pharmacological effect/associated reaction, which is also recognized with another concomitant therapy/illness or other external cause.
 - **PROBABLY RELATED**: appropriate temporal association, known pharmacological effect, recognized to be an associated IMP/BF-RhodoLED® reaction and for which no other possible cause is evident.
 - **DEFINITELY RELATED**: the reaction has occurred with this IMP/BF-RhodoLED® previously (i.e. positive re-challenge) and there is an appropriate temporal relationship between therapy and reaction; and the reaction follows a known or expected response pattern to the suspected drug.

The investigator should use medical judgment to determine whether he/she assumes a reasonable causal relationship, including into his/her evaluation all relevant factors and factual evidence such as

- temporal course and latency
- results from de-challenge or re-challenge
- pattern of the reaction
- known pharmacological properties of the product
- and alternative explanations (e.g. other drugs, medical history, concomitant diseases).

Every attempt should be made to describe the AE in terms of a diagnosis. If a clear diagnosis has been made, individual signs and symptoms will not be recorded as separate AEs unless they represent atypical or extreme manifestations of the diagnosis, in which case they should be documented as separate events. In the case of SAEs or SARs, respectively, component signs and symptoms may be recorded in addition to a diagnosis if they further clarify the clinical picture. If a clear diagnosis cannot be established, each sign and symptom must be recorded individually.

All subjects who have AEs, whether considered associated with the use of the IMP and/or the medical device or not, should be monitored to determine the outcome. The clinical course of the AE will be followed up according to accepted standards of medical practice, even after the end of the period of observation, until a satisfactory explanation is found or the investigator considers it medically justifiable to terminate FU. Should the AE result in death, a full pathologist's report should be supplied, if possible.

See [Section 8.2](#) for details on the observation period of AEs and SAEs or SARs, respectively.

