8.4 IMMEDIATE REPORTING BY INVESTIGATOR TO SPONSOR

8.4.1 Reporting of SAEs

SAEs during the clinical observation period as well as relevant SAEs or SARs during the follow-up phase must be documented on a ‘Serious Adverse Event/Expedited Report for Combination Products from a Clinical Trial form’ in accordance with instructions for completing the ‘Serious Adverse Event/Expedited Report for Combination Products from a Clinical Trial form’. This form and the instructions will be provided in the investigator file and must be completed and supplied immediately to the sponsor (21CFR§ 312.32, 21CFR§ 312.64).

Any SAE that occurs during the clinical observation period of the study, whether or not related to the IMP or the medical device, and any relevant SAE or SAR during the follow-up phase must be reported by the investigator within 24 h by fax, or by e-mail, to the following persons:

Email: [REDACTED]

Fax: [REDACTED]

The initial report must be as complete as possible, including details of the current illness and (serious) AE, and an assessment of the causal relationship between the event and the IMP(s) or medical device or study procedures.

Information not available at the time of the initial report (e.g. an end date for the AE or laboratory values received after the report) must be documented on a ‘Serious Adverse Event/Expedited Report for Combination Products from a Clinical Trial form’, with the box “Follow-up” checked under “Report type”.

The instructions for completing the ‘Serious Adverse Event/Expedited Report for Combination Products from a Clinical Trial form’ give more detailed guidance on the reporting of SAEs, AEs that comply with alert terms, and AEs initially reported as non-serious that become serious. In the latter situation, when a non-serious event becomes serious, details must be forwarded immediately to the sponsor on a “Serious Adverse Event/Expedited Report for Combination Products from a Clinical Trial” form.

Pregnancies occurring during a subject's participation in the study, although not typically considered SAEs, must be notified to the sponsor within the same timelines as an SAE (within 24 h after becoming aware of the pregnancy) on a pregnancy notification form. If possible, the clinical visits as well as the FU visits should be completed, but no further PDT must be applied. Further treatment will be addressed on a case-by-case basis with the treating physician and the investigator.

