#### Frequency and extent of TEAEs, including SAEs

TEAEs are defined as all AEs with time of onset on or after the time of treatment with randomized IMP within 4 weeks (28 days) after each PDT cycle. If time of onset of AEs is not within 4 weeks (28 days) after each PDT cycle, but is identified to be at least possibly related to IMP or medical device, AEs will be assumed as TEAEs. The reference dates will be calculated as date of last PDT within each PDT cycle + 28, i.e. date of PDT-2 and/or PDT-4, respectively. If PDT-2 and/or PDT-4 are not available, the dates of PDT-1 and/or PDT-3 will be used for calculation of reference dates. These reference dates will be used for assignment of TEAEs. If unclear due to incomplete start time/date of AE or PDT, AEs will be assumed as TEAEs, as far as end time/date of AE is not before first treatment in first PDT cycle. AEs and TEAEs will be summarized and tabulated according to primary system organ class and preferred term displaying the number of events as well as counts and percentages on a subject basis per treatment arm.

[figure not shown]
Additionally, TEAEs by sex, TEAEs by age group I, serious TEAEs and TEAEs by intensity (mild/moderate/severe/unknown) will be tabulated. Related TEAEs (defined as possibly, probably, or definitely related, or with missing relationship) will be presented by intensity overall (related to IMP or related to medical device), related to IMP only, related to IMP and medical device and related to medical device only. Additionally, TEAEs by relationship (unrelated / unlikely related / probably related / probably related / definitely related) will be presented related to IMP and related to medical device separately.

TEAEs leading to death and TEAEs resulting in discontinuation of study will be tabulated if more than 5 events are observed. Specification of any action taken documented on AE page as 'Withdrawal from study' will be used for detection of TEAEs resulting in discontinuation of study.

A listing of subjects with TEAEs will be provided for all TEAEs reported. Non-TEAEs, i.e. AEs with onset before treatment or later than 4 weeks after each PDT cycle, will be listed separately for all subjects enrolled. In listings, the start day of the AE relative to start of treatment will be calculated for complete start dates only. Duration of events is only calculated for complete start and end dates.

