#### Local reactions in the treatment field(s)

Local reactions, i.e. local skin reactions and local discomfort as assessed by investigator, are documented on AE page and can be identified as AEs with CRF question 'Is this (S)AE within a treatment field?' answered with 'yes' and are related (defined as possibly, probably, or definitely related, or with missing relationship) to IMP or medical device. Variable will be 'yes' if local reaction is documented at least once. Otherwise, variable will be 'no'. TEAEs identified as local reaction will be tabulated separately by intensity (mild/moderate/severe/unknown) separately for each PDT cycle. Therefore, local reactions with time of onset on or after the time of PDT-1 and before the time of PDT-3 will be categorized to PDT cycle 1. Local reactions with time of onset on or after the time of PDT-3 will be categorized to PDT cycle 2. If PDT-1 and/or PDT-3 are not available, the dates of PDT-2 and/or PDT-4 will be used for calculation respectively. If unclear due to incomplete start time/date of local reactions or PDT, local reactions will be categorized to PDT cycle unknown. Furthermore, the worst intensity (none/mild/moderate/severe) of at least one occurred PTs will be presented for local reactions. Thereby not available local reaction will be presented as intensity none. Missing or unknown intensity will not be considered for worst intensity analysis. Additionally, the frequency of any TEAEs identified as local reaction will be presented together with the respective CIs for each treatment group.

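### An adverse event caused only by the mandatory excision cannot be coded UNRELATED and has no procedure category, so it can be tabulated as related to drug or lamp

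*Protocol*

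**What the plan says.** Protocol 8.1.1 lists among its examples of adverse events "An effect of an invasive procedure required by the protocol". The Main Target Lesion excision, mandatory for every subject, is such a procedure, and so is the screening biopsy.

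On causality the protocol uses three frames of reference:

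- Section 8.1.2: "Any adverse event should be assigned to be unrelated or related to either the study medication, the medical device", or both. The opening of 8.3.1 says the same. Study procedures are not mentioned.
- The causality scale in 8.3.1: UNRELATED requires a cause "clearly and incontrovertibly due to a cause other than the IMP/BF-RhodoLED® and study procedure". The AE details required in the same section include "source (study medication/device/both", and a later item allows drug only, device only, or not assignable between the two. Neither offers a procedure.
- Section 8.4.1, for initial SAE reports only: "an assessment of the causal relationship between the event and the IMP(s) or medical device or study procedures".

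SAP 4.5 treats possibly, probably, definitely and missing as related; UNRELATED and UNLIKELY are not. An event outside the 28-day window that "is identified to be at least possibly related to IMP or medical device, AEs will be assumed as TEAEs". A local reaction is an event answered yes to "Is this (S)AE within a treatment field" and rated as related, or with the rating missing. The SAP tabulates relationship to IMP and to device, with no procedure category.

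**The concern.** The word procedure in the UNRELATED definition works against the purpose of the scale. Take a wound event that the investigator is certain the surgeon caused. It fails UNRELATED because its cause is a study procedure, and no other category describes it. Two sites following different parts of the protocol would code it differently: one reading 8.1.2 would call it unrelated, and one reading the causality scale could not.

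The related-event and local-reaction tables are meant to describe the drug and the lamp in a trial that seeks a label extension. If some surgical events enter them through a coding gap, those tables overstate drug or device reactions by an unknown amount that depends on site habit.

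**Working it through.** The documents give no figure to reproduce. The check traces the wording through the table definitions and uses the visit schedule to see which events can reach the tables.

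**Step 1: which codes are open to an event caused solely by excision?**

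| Code (Protocol 8.3.1) | Does it fit? | Related under SAP 4.5? |
|---|---|---|
| UNRELATED | No, because the cause is a study procedure | No |
| UNLIKELY | Imperfectly. It covers another cause being present, but expects atypical timing and no known response pattern, and presumes the drug's role cannot be ruled out | No |
| POSSIBLY | Can fit where the sign is a known drug or lamp reaction that also has an outside cause | Yes |
| Left blank | Plausible when nothing fits | Yes, in the related-TEAE tables and the local-reaction variable |

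Protocol 1.2 (risk-benefit analysis) lists erythema, edema, scab, discharge and pain during illumination among the expected effects of treatment. The first four could also appear at an excision site, so the pattern criterion for UNLIKELY is hard to meet on signs alone.

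**Step 2: where do the excision dates fall relative to the TEAE window?** Inputs: PDT-2 is 1-2 weeks after PDT-1, Visit 5 is 12 ± 1 weeks after PDT-1 (Protocol 3.1), and the window closes 28 days after the last PDT of the cycle (SAP 4.5). With PDT-1 as day 0:

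- PDT-2: day 7 to 14.
- Window closes: 7 + 28 = 35 to 14 + 28 = 42.
- Visit 5: 84 - 7 = 77 to 84 + 7 = 91.
- Gap from window close to Visit 5: 77 - 42 = 35 to 91 - 35 = 56 days.
- Time from last PDT to excision: 77 - 14 = 63 to 91 - 7 = 84 days.

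The same intervals apply to Visit 8, counted from PDT-3.

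**Step 3: which events reach the tables?**

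- *Screening biopsy.* Events starting before PDT-1 are non-TEAEs under SAP 4.5 and are listed separately. They do not reach the related-TEAE or local-reaction tables.
- *Complete responders excised at Visit 5, and Main Target Lesions excised at Visit 8.* AE collection ends at that visit (Protocol 8.2), and SAP section 4 drops events starting after the last clinical-phase visit or assessment. In essence, only events starting on that date remain. They lie outside the 28-day window and become TEAEs only if rated at least possibly related. A blank rating is not named in that extension.
- *Partial responders whose Main Target Lesion is clear at Visit 5 while another lesion is not.* The lesion is excised that day before PDT-3 (Protocol 5.1.2), and AEs are collected until Visit 8. Events starting after PDT-3 and within the cycle-2 window (up to 35-42 days after PDT-3) are TEAEs whatever their cause. The rating then decides whether they enter the related tables and, inside a treatment field, the local-reaction variable. Here a blank also counts as related. Events after that window enter only if rated at least possibly related.

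The main exposed group is therefore the third one. It is limited to subjects with at least two target lesions and a mixed response at Visit 5. The documents do not say how many to expect.

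**The case against.** The strongest objection is that failing UNRELATED does not make an event related. UNLIKELY exists, mentions another causative factor, and stays outside the SAP's related set. Protocol 8.3.1 also asks for medical judgment on timing, pattern and alternative explanations. Section 8.1.3 says most reactions occur during illumination or shortly afterwards and usually last 1 to 4 days, though some persist for 1 to 2 weeks or longer. A new wound event 63 to 84 days after the last PDT is atypical in time, and many investigators would choose UNLIKELY. This stands for most excisions. It is weaker when excision and PDT-3 fall on the same day. Even there, only uncleared lesions are retreated, so the excised site receives no PDT-3 and location helps separate the causes.

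A reader might infer that biopsy and excision effects are systematically pushed into the related and local-reaction tables. The documents do not support that: pre-IMP biopsy events cannot get there, most excisions coincide with the end of AE collection, and UNLIKELY remains open.

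A reader might also apply an assumed event rate to all excisions, taking 186 × 0.9 = 167 of them. That count has no basis in the documents. The 10% is the planned share with missing histology, not with no excision, and the AE cut-off removes most later events. An imbalance between arms is conceivable, because excision timing depends on response, but nothing in the documents shows one.

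Finally, the eCRF and the sponsor's detailed AE instructions are not among the documents, so the lack of a procedure item can be judged only from the protocol's list of required details.

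**Conclusion.** The point holds in limited form. The causality scale in 8.3.1 conflicts with 8.1.1, 8.1.2, its own section's opening and the SAE report content in 8.4.1. It denies an event caused solely by excision its correct code. SAP 4.5 then has no procedure category, so such an event can be reported as related to drug or device, or as a local reaction, if it is rated possibly or, when already treatment-emergent, left blank.

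The exposure is events starting on the excision-visit date and, mainly, events in partial responders excised at Visit 5 before PDT-3. Its size cannot be computed from the documents. The safety analyses are descriptive, and no confirmatory test is affected. Any error would overstate drug or device reactions rather than hide them. This conclusion assumes that the eCRF follows the protocol's list and that the sponsor's separate instructions do not already resolve the conflict.

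**What to change.** 1. In Protocol 8.3.1, define UNRELATED against the IMP and the device only, in line with 8.1.2 and the opening of 8.3.1.
2. Add study procedure (biopsy or excision) as an attribution item in the required AE details. If the eCRF can no longer change, identify these events at the blind data review described in SAP 4.8, before unblinding.
3. In SAP 4.5, keep events attributed solely to a study procedure out of the related-TEAE tables, the related-event extension of the TEAE window and the local-reaction variable. Show them by arm in a separate row so that nothing disappears from the report.

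The cost is one definition, one data item, a few lines of SAP text and one table row. The downside is one more attribution per adverse event for the sites.
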